Trimosan is a vaginal gel, with a pH of 4, marketed to help restore and maintain the normal vaginal acidity and coats the walls of the vagina with a lubricating film that helps reduce odor causing bacteria (8). There are not yet any published trials regarding Trimo-San's efficacy.

Bacterial vaginosis occurs in a setting of vaginal pH > 4.5, with peak adherence to vaginal mucosa occurring at pH 5 -6 (6).

There are previous papers which suggest that acidifying gels have been able to treat BV and prevent recurrence compared to placebo in its ability to acidify the vaginal pH. (Successful treatment of bacterial vaginosis with a policarbophil-carbopol acidic vaginal gel; recurrent bacterial vaginosis: the use of maintenance acidic vaginal gel following treatment). Given these suggestive findings, it goes to follow that Trimo-san may also be effective in decreasing pH and bacterial vaginosis infections.

In one study, vaginal pH of 6.0 to 7.5 is strongly suggestive of menopause (13). While it is known that estrogen can reduce vaginal pH and that Trimo-san may potentially do the same, these creams have never been studied in the context of pessary users.

Objectives:

Study hypothesis: In postmenopausal pessary users, estrogen users will have a more acidic pH, less complaints of vaginal discharge/odor, and decreased rates of bacterial vaginosis, than trimosan users.

Primary objective: vaginal pH with both treatment arms, as measured by pH test strips

Secondary objective: to see difference of patient satisfaction between treatment arms as measured by an unvalidated vaginal symptoms questionnaire.

Tertiary objective: rate of bacterial vaginosis infection (to be diagnosed either by gram stain (Nugent Score) or BV Affirm.

Study Design:

- 1) Randomized controlled
- 2) Study duration: 1 year 3 years.
- 3) Subject duration: 3 months
- 4) Assessment of efficacy: Cost savings, future increase in compliance as less medication may be needed overall, possible decrease in bacterial vaginosis infection
- 5) Assessment of safety: Estrogen Side effects abnormal vaginal bleeding, nausea, breast tenderness, bloating. Otherwise, low risk study.

Study Population:

6) Number of subjects to be enrolled? 34. 17 in each arm. Power 80%. P value: 0.05 P value 0.5. Power 80%. Sample size calculated with the expectation that estrogen will drop vaginal pH to 5.5 and Trimosan will decrease vaginal pH to 4.5.

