- Recruitment: Will recruit 44 patients (assuming 15% non enrollment, and 15% drop out) This study will be open to all clinic patients at Harris Health (LBJ, Aldine, BT Clinics), UT Houston clinics (Memorial Hermann, Sugarland, Memorial City),
- 8) All participants will read and sign The Certificate of Informed Consent when they arrive at the designated testing site, prior to their participation in the research procedure. After the participants have finished their participation in the study, or once they have decided to withdraw from the study, they will be given a verbal and written debriefing statement.
- 9) Inclusion:
 - Postmenopausal female pessary user (ring with support pessaries only) 18 years and older. Postmenopausal defined as: 1) amenorrhea for a year 2) 3 months after surgical bilateral salpingo-oophorectomy
 - Is a new pessary user, or has not had a pessary for a year
- 10) Exclusion:
 - Pregnancy
 - o Persistent Bacterial Vaginosis infection in the first two clinic encounters
 - Currently on hormone replacement therapy
 - Previously on hormone replacement therapy in the past 6 months
 - o Currently on antibiotics
 - Patients with existing vaginal erosions/ulcerations

Study Procedures:

Estrogen Treatment Arm: Will use either Premarin or Estrace cream (dependent on patient's insurance). Premarin 1 gram every night for the first 7 days, then 0.5 grams twice weekly. Estrace cream – 2 grams daily for first 7 days, then 1 gram twice-weekly.

Trimosan Treatment Arm: ½ applicator for three times a week for 1st week, then ½ applicator for 2 times a week.

The procedures are different because of funding/resources differences at Harris Health Clinics versus UT clinics. At Harris Health, they can be fitted for a pessary, but they must then take a prescription to an outside pharmacy in order to buy their personal pessary, and must come back to have it placed. At UT clinics, they have a ready stock of pessaries that the patients may purchase at the time of their fitting.

For Harris Health and BT Clinics:

1st encounter - Clinic visit to fit pessary from kit, pessary will be ordered, vaginal pH collected, vaginal gram stain collected, pt will fill out questionnaire, and be randomized to a treatment arm.

2nd encounter – Clinic visit to have their own pessary inserted, and be advised treatment according to which treatment arm they were randomized to.

3rd encounter – Clinic visit in 2 weeks after pessary fitting to evaluate vaginal tissue and symptoms.

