4th encounter – Telephone call (6 weeks after personal pessary fitting) – to remind patient of their next visit and compliance with treatment.

5th encounter - 3 month clinic visit – vaginal pH to be collected, vaginal gram stain, will fill out questionnaire. Exit process explained and standard of care for pessary users will be continued.

For UT clinics:

1st encounter: Patients will be fitted for a pessary, and their own pessary will be placed, consented, fill out questionnaire, vaginal pH collected, BV affirm collected, randomized to a treatment arm, cream will be prescribed.

2nd encounter: Clinic visit in 2 weeks after pessary fitting to evaluate vaginal tissue and symptoms.

3rd encounter – telephone call – 6 weeks after initial pessary fitting to remind patients of next visit and compliance with creams

4th encounter – 3 month clinic visit: vaginal pH to be collected, BV affirm to be collected, will fill out questionnaire. Exit process explained and standard of care for pessary users will be continued.

Data and Safety Monitoring:

- 11) No adverse events expected
- 12) Plans for reporting unanticipated problems: ***
- 13) Safety monitoring plan periodic review by research team

Statistics: Level of significance p 0.5

Ethics

- IRB approval will be sought from CPHS.

The PI will see the patient. If the PI thinks that the patient may qualify for a study, she will communicate basic information to the patient and will inform the patient that the research coordinator will talk to her. The research coordinator will gather the pertinent information and will talk to the patient. If the patient agrees to hear about the study, the patient will be moved to a private room, if applicable. The PI will explain the consent form in the patient's native language provided that language is either English or Spanish. Other languages will require a consent form translated into the patient's native language. The PI will explain the study through the consent form page by page and will give the patient plenty of time to read the form and ask questions. If the patient agrees to participate then both the patient and the PI will sign the ICF and a copy will be given to the patient. Then in accordance with the protocol, the INC/EXC criteria will be revised and the screening test will be scheduled at the patient's convenience.

Data handling and record keeping

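### Two clinic systems follow different pathways, but neither allocation nor analysis accounts for system; the cost is avoidable chance imbalance and lost precision, not bias

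*Combined protocol and SAP*

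**What the plan says.** Under Study Procedures the protocol explains why there are two pathways: "The procedures are different because of funding/resources differences at Harris Health Clinics versus UT clinics". Harris Health patients buy the pessary at an outside pharmacy and return to have it placed; UT clinics hold stock.

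- **Harris Health and BT.** At the first encounter pH and a gram stain are taken, and the "pt will fill out questionnaire, and be randomized to a treatment arm". The woman's own pessary and her treatment advice come at the second encounter. There are five encounters.
- **UT.** Pessary placement, questionnaire, pH and the rest happen at one visit: "BV affirm collected, randomized to a treatment arm, cream will be prescribed". There are four encounters.

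BV is assessed by gram stain at Harris/BT and by BV Affirm at UT. The primary outcome, vaginal pH by test strip, is taken at the first encounter and at 3 months in both systems.

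On allocation, Study Design says only "Randomized controlled", and the two pathways say only that women are randomised to an arm. No strata, blocks or site lists appear. The statistics section consists of "Statistics: Level of significance p 0.5", with no test, model or covariate. Under Study Population the size is "34. 17 in each arm".

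**The concern.** Clinic system is known before randomisation, and the protocol itself says the pathways differ. If system is related to 3-month pH, leaving it out has two consequences. An uneven split of UT women between arms carries part of the system difference into the arm difference. In a plain two-group comparison, the system difference also stays in the residual variance.

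A relation with pH is plausible from the pathways. Harris women start treatment later after randomisation, and the 3-month visit has no stated starting point, so time on treatment at the pH reading may differ. The exclusion for BV persisting over the first two encounters covers a period before treatment advice at Harris, but a period that includes treatment at UT. The estrogen product depends on insurance, which might follow the clinic system, although the protocol does not say so. None of this shows that pH differs by system.

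The BV outcome is affected more directly, because the assay itself changes with system. An imbalance in system between arms is then also an imbalance in assay.

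**Working it through.** **Inputs from the protocol.** Two arms of 17; means of 5.5 and 4.5 ("estrogen will drop vaginal pH to 5.5 and Trimosan will decrease vaginal pH to 4.5"), a difference of 1.0 pH; 80% power. Alpha is given inconsistently ("Power 80%. P value: 0.05 P value 0.5. Power 80"); 0.05 two-sided is used here.

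**Assumptions.** The protocol gives no SD, no split of women between systems and no between-system pH gap *d*. I take SD = 1.0, half the women UT (17 of 34), and *d* = 0, 0.5 or 1.0.

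**1. The plan's sample size.** Without an SD, 34 cannot be derived from the stated inputs. With SD 1.0, the normal formula n = 2 × (1.960 + 0.842)² × SD² / 1.0² = 15.7 gives 16 per arm. The t-test power at 17 per arm is 0.807. So 34 is consistent with an SD of about 1.0.

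**2. Chance imbalance.** With 17 UT women and arms of 17, the number of UT women in one arm is hypergeometric. The difference in UT count between arms can only be 1, 3, 5, 7 and so on.

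| UT women by arm | Difference | Chance of at least this |
|---|---|---|
| 10 vs 7 | 3/17 = 17.6 points | 49.4% |
| 11 vs 6 | 5/17 = 29.4 points | 16.9% |
| 12 vs 5 | 7/17 = 41.2 points | 3.8% |

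With 10 UT women in place of 17, the chance of at least 4/17 (7 vs 3, 24 points) is 26%, and of at least 6/17 (8 vs 2, 35 points) 6%.

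**3. Shift in the arm difference** = *d* × imbalance.

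- At 5/17: 0.5 × 0.294 = 0.15 pH; 1.0 × 0.294 = 0.29 pH.
- On average: the mean absolute imbalance is 0.142, so the mean absolute shift is 0.07 pH at *d* = 0.5 and 0.14 pH at *d* = 1.0.

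**4. Power, if 1.0 is the within-system SD.** Unadjusted total SD = √(1 + 0.25*d*²), and SE = SD × √(2/17).

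| *d* | Total SD | SE | Unadjusted power | Stratified and adjusted |
|---|---|---|---|---|
| 0 | 1.000 | 0.343 | 80.7% | 80.6% |
| 0.5 | 1.031 | 0.354 | 78.3% | 80.6% |
| 1.0 | 1.118 | 0.383 | 71.5% | 80.6% |

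The adjusted column uses SE 0.343 and 31 degrees of freedom in place of 32. Simulation with 34 women agrees: 0.81, 0.78 and 0.72 unadjusted; 0.80 to 0.81 adjusted.

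**5. Power, if 1.0 is the total SD.** The within-system SD is then √(1 − 0.25*d*²) = 0.968 at *d* = 0.5 and 0.866 at *d* = 1.0. Unadjusted power stays at about 80 to 81%. Stratifying and adjusting raises it to 83% and 90%.

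**6. Type I error.** In simulation the unstratified, unadjusted test stays between 0.049 and 0.052. Stratifying the allocation but leaving system out of the test makes the t-test conservative: 0.045 at *d* = 0.5 and about 0.03 at *d* = 1.0. With the system term it returns to about 0.05.

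**The case against.** The strongest case against is that nothing in the documents links system to the primary outcome. The stated reason for the two pathways is pessary supply; pH is read by test strip at the same two points in both; regimens are set by arm, not by system; and the background says a pessary does not change the microbial environment. This stands: the system effect on pH is an assumption, and its size is unknown.

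The effect is also small in the moderate case. At a gap of 0.5 the 0.15 pH shift is 0.147/0.343 = 0.43 of a standard error and needs an imbalance that arises in 17% of allocations. The 72% power figure needs a system gap as large as the planned treatment difference. Both points stand.

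A reader might infer that the primary result would be biased or its false-positive rate raised. It would not: chance imbalance is already reflected in the standard error. A reader might also take the fall from 81% to 78% or 72% as an established loss. It is a loss only if the SD behind the sample size is the within-system one; if it is the total SD, planned power is intact and adjustment is a gain. Nor should 17.6 points be rounded up and read as a threshold: the chance of a difference of at least 18 points is 17%, not 49%.

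Finally, because no pH analysis is specified at all, system is omitted by silence and not by a stated choice. Step 4 assumes a plain two-group comparison.

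**Conclusion.** The point holds as a matter of precision and avoidable chance imbalance. The protocol describes two pathways and takes system into account neither in allocation nor in any stated analysis. The trial remains valid without a change.

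Under the stated assumptions (half the women UT, SD about 1.0, two-sided 0.05), the consequence is minor for a gap of 0.5 pH or less: about 2 points of power and a typical shift of 0.07 pH. It becomes material only near a gap of 1.0 pH: about 9 points of power, and 0.29 pH at a 5-woman imbalance. For BV the reason to act does not depend on an assumed pH gap, since the assay differs by system.

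A reader might also infer from the investigator's role in judging eligibility and taking consent that assignments could be foreseen. The protocol is silent on concealment, but that is a separate selection question which these figures do not address; it should be raised on its own and lends no weight here. This is a suggestion, not a required correction.

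**What to change.** Make both changes together, since stratifying without adjusting gives a conservative t-test:

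1. Randomise 1:1 in permuted blocks of varying size within two strata, Harris Health/BT and UT.
2. Specify that the 3-month pH comparison includes clinic system as a two-level term, and that the BV comparison is stratified by system, so that arms are compared within the same assay.

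The cost is a protocol sentence for the allocation and one for the analysis, a two-stratum list and one degree of freedom. If the systems do not differ in pH, power goes from 80.7% to 80.6%. No extra women are needed and no treatment procedure changes.

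### At the Harris/BT clinics women are randomised one visit before they have their own pessary or are advised on treatment, so some can be lost or excluded between allocation and treatment

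*Combined protocol and SAP*

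**What the plan says.** The Study Procedures section gives two schedules and explains that they differ because of resources.

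- **Harris Health and BT, 1st encounter.** The woman is fitted from a kit, the pessary is ordered, pH and gram stain are taken, and "pt will fill out questionnaire, and be randomized to a treatment arm".
- **Between visits.** Harris patients "must then take a prescription to an outside pharmacy in order to buy their personal pessary, and must come back to have it placed". No interval or limit is given.
- **Harris Health and BT, 2nd encounter.** "Clinic visit to have their own pessary inserted, and be advised treatment according to which treatment arm they were randomized to".
- **UT, 1st encounter.** The woman's own pessary is placed, baseline measures are taken, and she is "randomized to a treatment arm, cream will be prescribed".

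The exclusion criteria include bacterial vaginosis that persists across a woman's first two clinic encounters. The Recruitment item allows 15% for non-enrolment and 15% for dropout, with 44 to be recruited for a target of 34. The Statistics entry gives a significance level and nothing else: no analysis population, and no rule for women who are randomised but never treated.

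On timing, the third Harris encounter (and the second at UT) is a "Clinic visit in 2 weeks after pessary fitting to evaluate vaginal tissue and symptoms". The Harris telephone call is timed "6 weeks after personal pessary fitting". The 3-month visit, where the primary pH is taken, has no stated start date in either system.

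**The concern.** Allocation is best made as late as possible before treatment starts, because every woman counted after it belongs to the randomised comparison. At Harris a purchase and a return journey fall between the two. A woman who does not complete them is randomised but untreated and will probably have no 3-month pH. The plan does not say whether she is replaced, dropped or counted. The bacterial vaginosis criterion creates a second route out: at Harris the second of the two encounters it refers to comes after randomisation.

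Dropping such women is harmless only if the reason for loss is unrelated to arm. No blinding is described, and nothing says the allocation is withheld from the woman or the clinician until the second encounter. A decision not to return, or to exclude, could therefore be influenced by the arm. With 17 per arm, a few such losses matter.

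**Working it through.** **Order of events**

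| Step | Harris/BT | UT |
|---|---|---|
| Baseline pH, vaginosis test, questionnaire | Encounter 1 | Encounter 1 |
| Randomisation | Encounter 1 | Encounter 1 |
| Outside purchase and return | After encounter 1, no limit | None |
| Own pessary in place | Encounter 2 | Encounter 1 |
| Treatment advised or prescribed | Encounter 2 | Encounter 1 |

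The gap between randomisation and treatment is built in at Harris and absent at UT.

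**The plan's own figures.** From the Study Population section: 17 per arm, 80% power, expected pH 5.5 and 4.5, so a difference of 1.0. The significance level is printed both as 0.05 and as 0.5; two-sided 0.05 is used here. No SD is given. With an assumed SD of 1.0, a two-sample t-test with 17 per arm has 80.7% power, which matches the plan. The recruitment figure reproduces as 34 × (1 + 0.15 + 0.15) = 44.2, or 44.

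**Women randomised.** If non-enrolment comes before randomisation, 44 × 0.85 = 37.4.

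**Overall untreated loss** = Harris share × non-return rate among Harris women; both are assumed. With half the women at Harris and 10%, 20% or 30% not returning, the overall loss is 5%, 10% or 15%.

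**Case A: the planned 15% dropout is meant to absorb these losses, and no others occur.**

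- 5%: 37.4 × 0.95 = 35.5 evaluable, power 82.5%
- 10%: 37.4 × 0.90 = 33.7 evaluable, power 80.3%
- 15%: 37.4 × 0.85 = 31.8 evaluable, power 77.9%

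**Case B: the losses come on top of the planned 15% dropout.** The planned losses alone leave 44 × 0.85 × 0.85 = 31.8, already below 34. A further 10% leaves 31.8 × 0.90 = 28.6 evaluable and power of about 73%. Across a Harris share of 25% to 75% and non-return of 10% to 30%, the overall loss runs from 0.25 × 0.10 = 2.5% to 0.75 × 0.30 = 22.5%, and power from about 77% to about 66%.

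**The case against.** Randomising at the baseline visit is a legitimate design, the protocol explains why the systems differ, and the recruitment target already allows for dropout. If that allowance is meant to cover women who never return, the power cost is small (Case A). This stands as a limit on the size of the problem. It does not supply a rule for women randomised but untreated, and it does not address loss related to arm.

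Several stronger readings are tempting, but the documents do not support them:

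- *The Harris 2-week check may come before the pessary is in place.* Its reference to a pessary fitting is loose, but the encounters are numbered: insertion is the second and the check is the third.
- *The 6-week calls count from different events.* The UT call is timed "6 weeks after initial pessary fitting to remind patients of next visit", but at UT the initial fitting is the visit at which the own pessary is placed. Both calls count from own-pessary placement.
- *Harris women have less than 3 months of treatment at the primary visit.* If 3 months (13 weeks) ran from encounter 1 and purchase took an assumed 2 to 4 weeks, exposure would be 11 to 9 weeks. No passage says it runs from encounter 1, and the call that reminds the woman of that visit counts from own-pessary fitting. The anchor is unstated, not contradictory.
- *The delay biases the comparison.* It falls on both Harris arms, so by itself it favours neither.
- *Power falls from 80.7% to between 73.6% and 78.5%.* That subtracts the losses from 34 and ignores the planned 44.
- *Keeping 10% untreated women in the analysis dilutes the difference to 0.9 and power to 72.1%.* That needs a 3-month pH from women described as never returning. The likelier problem is missing data.

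**Conclusion.** The point holds for the timing of randomisation at Harris/BT. The schedule allows women to be randomised and never treated, or excluded after randomisation, and the plan does not say how they would be handled. Arm-related loss is a possibility left open by the absence of any described blinding; the documents do not show that it would occur.

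The effect on power ranges from negligible, if the losses fit within the planned dropout, to a drop of about five points (77.9% to about 73%) if 10% of randomised women are lost untreated in addition to it. These figures rest on an assumed SD of 1.0, Harris share and non-return rate, and on reading non-enrolment as loss before randomisation.

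The missing start date for the 3-month visit is a secondary matter of clarification. The change is worth making because it is cheap and the trial is small, but the trial could run without it.

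**What to change.** At Harris/BT, keep encounter 1 for fitting and baseline measures, and open the allocation at the existing encounter 2, once the woman has returned with her pessary and eligibility is confirmed. Analyse all women randomised from that point, and say so in the Statistics section.

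Reconcile the bacterial vaginosis exclusion with the schedules. No vaginosis test is listed at encounter 2 in either system, and at UT the second encounter would still follow randomisation, so moving the Harris allocation does not settle the matter there.

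Reconcile the timing passages so that the primary pH is measured from the same reference event in both systems, and make clear which event the Harris 2-week visit refers to.

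Cost: no extra visit. The allocation must be available at encounter 2. The Harris baseline pH, gram stain and questionnaire would precede randomisation by the purchase interval, but they already precede treatment by that interval. The plan should state whether the encounter 1 pH remains the baseline.

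### Item 5 makes four estrogen side effects the safety assessment, item 11 expects no adverse events, and no scheduled contact specifies asking about those effects

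*Combined protocol and SAP*

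**What the plan says.** Four places in the protocol bear on this point.

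- **Study Design, item 5:** "Assessment of safety: Estrogen Side effects abnormal vaginal bleeding, nausea, breast tenderness, bloating. Otherwise, low risk study".
- **Data and Safety Monitoring, items 11 to 13:** item 11 reads "No adverse events expected". Item 12 has the label "Plans for reporting unanticipated problems", followed only by asterisks in the public text. Item 13 reads "Safety monitoring plan periodic review by research team", with no frequency, content or data source.
- **Study Procedures, Harris Health and BT clinics:** the 3rd encounter is a "Clinic visit in 2 weeks after pessary fitting to evaluate vaginal tissue and symptoms". The 4th is a telephone call at 6 weeks, "to remind patient of their next visit and compliance with treatment". The 5th, at 3 months, lists pH, a gram stain and the questionnaire.
- **Study Procedures, UT clinics:** the same pattern. The 2-week visit is "2nd encounter: Clinic visit in 2 weeks after pessary fitting to evaluate vaginal tissue and symptoms", the call is "6 weeks after initial pessary fitting to remind patients of next visit and compliance with creams", and the 3-month visit lists pH, BV Affirm and the questionnaire.

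Under Objectives, the questionnaire is described as an unvalidated instrument on vaginal symptoms that serves the satisfaction objective. Its items are not in the documents. No safety summary or analysis is described.

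**The concern.** Item 5 tells the reader which events safety will be judged on. Item 11 tells site staff to expect none. The encounter lists, which are what staff will follow, do not say that anyone asks about the item 5 events.

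Events that nobody asks about cannot be recovered at the analysis stage. If the lists are followed as written, most of the item 5 assessment rests on what women volunteer. Item 5 also ties the effects to estrogen alone. No blinding is described, and the two arms use different products on different regimens, so women and staff may know the allocation. A bloating or nausea complaint may then be noted more readily in the estrogen arm, and a difference between arms could reflect attention rather than treatment.

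**Working it through.** The plan gives no figure for this point, so the main check sets the item 5 effects against each contact after treatment starts, in both clinic systems.

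| Contact | What is listed | Bleeding | Nausea, bloating, breast tenderness | Vaginal tissue |
|---|---|---|---|---|
| 2 weeks (Harris Health/BT 3rd, UT 2nd encounter) | Tissue and symptoms; symptoms not defined | Possible, not specified | Not specified; covered only if symptoms is read broadly | Yes |
| 6 weeks (Harris Health/BT 4th, UT 3rd) | Reminder and compliance | Not listed | Not listed | Not applicable (telephone) |
| 3 months (Harris Health/BT 5th, UT 4th) | pH, BV test, questionnaire | Possible, if the questionnaire includes it | Not listed; the questionnaire is described as covering vaginal symptoms | Not listed |

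Four results follow.

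1. None of the three contacts names any of the four effects. One of the four, bleeding, has a plausible route at two contacts. The other three are not vaginal symptoms and have no stated collection point.
2. Tissue evaluation is listed once, at 2 weeks. Item 10 excludes women with existing erosions or ulcerations at entry, but a lesion arising after the 2-week visit has no listed check.
3. Item 5 and item 11 conflict on their face, because a list of named side effects is a list of events that are thought possible.
4. Item 13 promises a review but does not say what data it receives.

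**Effect of uneven asking.** Let p be the true proportion with an effect, equal in both arms, and let a_E and a_T be the probabilities that an event is recorded in the estrogen and Trimosan arms. Expected recorded counts are 17 × p × a_E and 17 × p × a_T. Their ratio is a_E / a_T, whatever p is. With equal true rates, the whole of any expected difference comes from recording. The documents give no value for a_E or a_T, so the size of this effect cannot be stated.

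**What complete recording would deliver.** The input is 17 per arm (Study Population, item 6). The event rates are assumptions, since the documents give none.

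- Exact two-sided 95% upper limit with 0 events in 17: 1 − 0.025^(1/17) = 0.195, or 19.5%.
- Chance of at least one event at a true rate of 5%: 1 − 0.95^17 = 0.58.
- Chance of at least one event at a true rate of 10%: 1 − 0.90^17 = 0.83.

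Full recording would therefore support description, not a formal comparison. These figures bound what the change can achieve; the finding does not depend on them.

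**The case against.** The strongest reply is that the plan is less bare than it may look, and much of that reply stands.

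- **No contact could pick up any item 5 effect.** A reader might infer this, but the documents do not support it. Every woman has a 2-week visit covering tissue and symptoms, in both arms and both clinic systems. Bleeding falls naturally within that, and the undefined word symptoms could be read more widely. The questionnaire may also ask about bleeding; its items are not shown.
- **The trial cannot answer its own safety question, or would finish with no safety record.** Neither follows. The hypothesis and the three objectives concern pH, symptoms or satisfaction, and bacterial vaginosis. Safety is a stated assessment, not an objective. The 2-week evaluation would leave something for item 13 to review, and the quality-control section provides for weekly collection with verification against the medical record.
- **Only estrogen users would be asked.** The plan does not say so. The encounter lists do not differ by arm. Selective asking is a risk created by item 5's wording and the absence of a common form.
- **Items 5 and 11 can be read together.** Item 11 might mean that nothing is expected beyond the known estrogen effects. That reading is possible, but item 11 does not say it, so the text still needs reconciling.
- **Small numbers.** With 17 per arm even perfect collection is imprecise. That limits what the counts can show, but it is no reason to record them incompletely.

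After all this, three named effects still have no stated collection point, tissue is not listed for evaluation at 3 months, and item 13 has no stated data source. Verification against the medical record checks what was recorded; it does not elicit what was never asked.

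**Conclusion.** The point holds in a limited form. Items 5 and 11 are inconsistent and must be reconciled. None of the three post-start contacts in either clinic system specifies asking about the four effects that item 5 names. For nausea, bloating and breast tenderness there is no stated collection point at all; for bleeding there are two possible but unspecified ones. Side-effect counts by arm may be incomplete, or may differ because of who was asked.

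This rests on reading the encounter lists as the full description of what is done, and on the questionnaire being what its label says. If the unseen questionnaire asks about the four effects, the 3-month gap narrows, but the conflict between items 5 and 11 and the missing data source for item 13 remain. I place no weight on the asterisks after item 12, which may be an unfilled placeholder or removed text. The change is worth making before enrollment because unasked events cannot be recovered later.

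**What to change.** 1. Reconcile items 5, 11 and 13 with each other and with both encounter lists, so that the protocol makes one statement on which events are anticipated and how they are recorded.
2. Put the same short checklist of the four item 5 effects to every woman in both arms at the existing 2-week, 6-week and 3-month contacts, recording yes or no and the date.
3. Record vaginal tissue findings, including any erosion or ulceration, at the 2-week and 3-month clinic visits.
4. Report the counts descriptively by arm, without a formal test, and name them as the data supplied to the item 13 review.

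The cost is four yes/no questions at each of three contacts already scheduled, a tissue entry at two visits and one small descriptive table. No new visit, laboratory test or staff is needed. Contacts become slightly longer, and the counts will remain imprecise at 17 per arm.

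### The Statistics line sets the significance level at 0.5, almost certainly meant as 0.05, and the sample-size paragraph prints both values

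*Combined protocol and SAP*

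**What the plan says.** The Statistics section, which follows Data and Safety Monitoring, consists of a single line: "Statistics: Level of significance p 0.5". It names no test, no sidedness and no analysis model.

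The only other place that gives a significance level is Study Population, item 6, the sample-size paragraph. It gives 34 subjects, 17 per arm, and then "P value: 0.05 P value 0.5. Power 80" (per cent). Both values are printed, and nothing marks either as superseded. The same item gives the planning difference: "Sample size calculated with the expectation that estrogen will drop vaginal pH to 5.5 and Trimosan will decrease vaginal pH to 4.5". It gives no SD.

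The comparison that the threshold governs is in Objectives: "Primary objective: vaginal pH with both treatment arms, as measured by pH test strips".

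**The concern.** A significance level of 0.5 means that, when the two creams have the same effect on pH, the trial declares a difference half the time. No one plans a confirmatory comparison on that basis, so the line looks like a misplaced decimal point.

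The obvious remedy is to look for the value elsewhere, but the only other place prints both candidates. With no named test or further analysis text, nothing else in the document identifies the intended rule. A pH result with p anywhere between 0.05 and 0.5 could be reported as significant by citing the Statistics line, or as not significant by citing the first value in item 6. A threshold that can be chosen after the data are seen is not prespecified, and the protocol intends publication.

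**Working it through.** **1. The two places side by side**

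| Place | Significance level printed |
|---|---|
| Statistics (whole section) | 0.5 |
| Study Population, item 6 | 0.05 and 0.5 |

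Item 6 may be an edit whose strike-through was lost when the file was read. It also prints the power twice, and Study Design, item 2 shows the same pattern: "Study duration: 1 year 3 years". There are then two readings:

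- If 0.05 is live in item 6, the Statistics line contradicts it.
- If 0.5 is live in item 6, the two places agree on a 50% threshold.

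Neither reading makes the Statistics line acceptable. That line has no doubled text, so a lost strike-through cannot explain it.

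**2. Size, from the printed values alone**

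With no true difference, the p-value is uniform between 0 and 1. So P(0.05 < p < 0.5) = 0.50 − 0.05 = 45%, whatever the SD. The nominal type I error is 50% under one value and 5% under the other.

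**3. Which value does 17 per arm fit?**

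Inputs from item 6: 17 per arm, 80% power, difference 5.5 − 4.5 = 1.0. Assumed, because not stated: a two-sided two-sample t-test and the SD.

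The normal approximation is n per arm = 2·SD²·(z₁₋α/₂ + z₀.₈₀)² / δ². At SD 1.0:

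- α = 0.05: 2 × (1.960 + 0.842)² = 15.7, so 16
- α = 0.5: 2 × (0.674 + 0.842)² = 4.6, so 5

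The exact t-test gives 17 at α = 0.05 and 5 at α = 0.5. The plan's figure of 17 is therefore reproduced at 0.05 with SD 1.0, and not at 0.5.

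Solving the other way, the SD at which 17 per arm gives exactly 80% power by t-test is 1.01 at 0.05 and 1.99 at 0.5.

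**4. Power and disagreement over a range of SDs**

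With df = 2 × 17 − 2 = 32, the critical t is 2.037 at 0.05 and 0.682 at 0.5. The noncentrality is (1.0/SD)·√(17/2) = 2.915/SD, and power is P(|T| > critical t) under the noncentral t. The share of trials in which the two thresholds disagree is the power at 0.5 minus the power at 0.05.

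| Assumed SD | Power at 0.05 | Power at 0.5 | Disagreement if the true difference is 1.0 |
|---|---|---|---|
| 0.7 | 98.1% | 99.97% | 1.9% |
| 1.0 | 80.7% | 98.7% | 18.0% |
| 1.5 | 47.0% | 90.1% | 43.1% |
| 2.0 | 29.3% | 79.8% | 50.5% |

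A simulation of 200,000 trials at SD 1.0 gave disagreement in 45.0% with no difference and 18.1% with a difference of 1.0, in agreement with the formulas.

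**The case against.** The strongest reply is that this is a typing error that every reader will correct. The conventional 0.05 is printed in item 6, and nothing shows that anyone would test at 0.5. It is probably true that 0.05 was meant, but that concedes the text is wrong. The 0.05 in item 6 is also an input to the sample size, printed next to its rival, and not a stated rule for the analysis.

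A second reply is that the doubling in item 6 may come only from reading the PDF. That is possible, and the point does not rest on item 6. If the 0.5 there is already struck out in the source, half of the fix is done.

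Third, the SD-dependent figures rest on assumptions, and the SD of 1.0 is close to the value back-solved from 17 per arm, so its fit to 0.05 is not independent evidence. This stands. Only the 5% against 50% contrast and the 45% share come from the printed values alone.

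Fourth, two-sidedness is the reviewer's choice, and the study hypothesis is directional. That also stands. However, the hypothesis expects a more acidic pH on estrogen, while item 6 plans for a lower pH on Trimosan, so the documents give no consistent direction for a one-sided test.

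Fifth, if 17 per arm was in fact derived at 0.5 with an SD near 2.0, correcting the level to 0.05 leaves 29.3% power, and 80% would need 64 per arm. This is a good reason to ask where 17 came from, but no reason to leave a 50% threshold in place.

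**Conclusion.** The concern holds, and the line must be corrected before the pH data are analysed. As written, the only significance level given for the analysis carries a nominal type I error of 50% on the primary comparison, and the sample-size paragraph does not resolve it. With no true difference, the two printed thresholds would give opposite conclusions in 45% of trials. With the planned difference of 1.0, the share is 18% at an assumed SD of 1.0, ranging from 1.9% at SD 0.7 to 51% at SD 2.0 (two-sided t-test assumed).

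That 0.5 is a slip for 0.05 is very probable but not proved. It rests on convention, on 0.05 appearing in item 6, and on 17 per arm matching 0.05 at SD 1.0. That the Statistics line is wrong as written does not depend on any assumed SD.

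**What to change.** Change the Statistics line to a significance level of 0.05, two-sided, and say that two-sided is adopted by convention. Delete the 0.5 from Study Population, item 6, so that both places carry the same single value.

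At the same time, the sponsor should confirm which significance level, SD and test produced 17 per arm, and state them in item 6. This is a useful addition and not a condition for the correction.

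The cost is two wording edits by amendment. The edits themselves change no visit, measurement or enrolment number. The sample size would need another look only if the sponsor finds that 17 was derived at 0.5.
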